17.4.8. For the above services, how many visits did you receive per week?

- 1    2    3    4  
 5 or more

---

17.4.9. For the above services, how many visits did you receive per week?

- 1    2    3    4  
 5 or more

---

17.5. Have you received other healthcare services since the last assessment ?

- Yes    No

---

17.5.1 If Other, please state

---

---

17.6 Have you received other healthcare services since the last assessment

- Yes    No

---

17.7 State what other services you have received

---

---

17.8.1 Have you received any personal care/home help since your last assessment?

- Yes    No

---

17.9.2 How often have you received home help?

- Daily  
 2 to 3 times per week  
 once a week  
 once a fortnight  
 once a month or less

---

17.10.1 Do you receive any other type of help?

- Yes    No

---

17.11.2. State what other help you receive.

---

---

17.12 Has there been a change in your employment status since your TIA/stroke?

- Yes    No

---

17.12.1 What changes have occurred since your last assessment?

- Newly employed  
 No longer employed  
 Reduced hours  
 Changed job or type of work  
 Now self-employed  
 Other

---

17.12.2 Please explain answer to 17.12.1

---

---

17.13 Are you currently in paid employment?

- Yes    No

---

17.13.1. If Yes to 17.13., what number of hours have you usually worked in the past 2 weeks?

---

---

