### 11. SECONDARY AIMS

The **secondary aims** are to determine the effectiveness of HWC in improving

1. Overall cardiovascular disease (including stroke) risk at 6 months post-randomisation based on the LS7 compared to Baseline

2. Individual LS7 behavioural risk factors at 3-, 6- 9- and 12- months post-randomisation compared to Baseline
3. Awareness about stroke symptoms, risk factors and their management 6- and 12- months post-randomisation compared to Baseline
4. Quality of life, at 6- and 12- months post-randomisation compared to Baseline
5. Cognitive outcomes at 6-, and 12- months post-randomisation compared to Baseline
6. Mood outcomes compared to Baseline
7. Adherence to CVD medications at 3, 6-, and 9 and 12- months compared to Baseline
8. CVD/adverse outcomes at 12 months post randomisation.
9. Health and service costs at 12 months post randomisation
10. Productivity status at 12 months post randomisation

Secondary outcomes are:

1. systolic blood pressure, total cholesterol, blood glucose at 6-months post randomisation
2. change in proportion of participants in 'high' and 'intermediate' to 'low' risk on LS7 at 6-months post randomisation
3. Stroke risk from Stroke Riskometer – 5- year absolute and relative risk at 6- and 12-months post randomisation
4. Quality of life (EQ5D) at 6-months post randomisation
5. Stroke awareness at 6- and 12-months post randomisation
6. Cognitive assessment score (Montreal Cognitive Assessment)
7. Medication adherence (Self-Efficacy For Appropriate Medication Use Scale (SEAMS))
8. CVD adverse outcomes (fatal and nonfatal stroke, TIA, myocardial infarction and heart failure, death attributable to CVD and all-cause mortality)
9. Healthcare and community service costs assessed as self-reported service use questionnaire at follow up. Productivity status will be self-reported and will include items regarding status (e.g., paid work, voluntary work, homemaker, student, unemployed), hours (e.g., full/part time), compared to hospitalisation pre-stroke status.

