**Section 6: Demographic Information**

6.1. Employment Status prior to stroke/TIA  Full-time: Paid employment for  $\geq 30$  hrs a week  Part-time: Paid employment for 1 to less than 30 hrs a week  Not in Paid Employment OR Paid employment for less than 1 hour per week  Retired

6.2. Current marital status  Married, civil union or de facto relationship  Single  Separated, divorced, or widowed

6.3. Usual dwelling place of participant prior to stroke/TIA  Own home  Rented  Living with friends or family  Retirement village or similar  Boarding house  Other  Unavailable

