**Section 17. Health Service Use (3, 6, 9 and 12 months)**

17.1. Have you visited your GP since your stroke/TIA  Yes  No

17.1.1. If Yes, how often since your TIA/stroke?  Once  
 Twice  
 Three times  
 Four times  
 More than 4 times  
 Can't remember

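### The follow-up hours item gives no unit against weekly baseline bands, and the job-change items mix two reference periods, so the hours part of the productivity outcome can be misread

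*Protocol*

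**What the plan says.** Section 11 (Secondary aims) of the protocol lists "Productivity status at 12 months post randomisation" as aim 10. Secondary outcome 9 adds that "Productivity status will be self-reported and will include items regarding status", together with "hours (e.g., full/part time), compared to hospitalisation pre-stroke status". The Health Economic Evaluation section gives lost productivity as an example of an indirect cost.

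The data come from the case record forms in Appendix C:

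- **Before the event.** Form B, item 6.1 records bands only. Full-time is 30 or more hours a week. The next band is "Part-time: Paid employment for 1 to less than 30 hrs a week".
- **Hours at follow-up.** Form F, item 17.13.1 asks those in paid work "what number of hours have you usually worked in the past 2 weeks". No unit is given. The copy of Section 17 in Form B has the same wording.
- **Job change at follow-up.** Item 17.12 asks "Has there been a change in your employment status since your TIA/stroke". Item 17.12.1 then asks "What changes have occurred since your last assessment". Its options are five kinds of change plus Other. Item 17.12.2 is a free-text explanation.
- **Timing.** The section is headed "Section 17. Health Service Use (3, 6, 9 and 12 months"), which is four follow-up visits.

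**The concern.** The outcome compares hours after the event with the pre-stroke state, so the two must be on the same scale. Baseline is per week. In the follow-up item, the word for usual work invites a weekly figure, while the two-week window invites a total. Both answers are truthful, and the form does not record which was meant. A conversion rule written later works only if everybody answered in the same way.

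The job-change pair has a different fault. The lead question is cumulative from the index event and its follow-on covers only the last interval. Someone whose job changed early answers Yes correctly at every later visit, and is then shown only kinds of change to choose from.

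At stake are false moves between full-time and part-time, error in the hours used for lost-productivity costs, and uncertainty over when or how often a job change happened.

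**Working it through.** The plan states no figure on this point to reproduce. The check sets the items against each other and uses simple arithmetic.

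**1. The factor of two.** Let *w* be true weekly hours. The answer is *w* if the item is read as a usual week and 2*w* if read as a two-week total. For *w* = 37.5 the entry is 37.5 or 75.

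**2. Misclassification at the 30-hour cut in Form B, item 6.1.**

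| Analyst treats all answers as | Participant gave | Value compared with 30 | Wrongly coded when |
|---|---|---|---|
| two-week totals (halved) | weekly hours *w* | *w*/2 | *w* ≥ 30 and *w*/2 < 30, so 30 ≤ *w* < 60: full-time coded part-time |
| weekly hours | two-week total 2*w* | 2*w* | *w* < 30 and 2*w* ≥ 30, so 15 ≤ *w* < 30: part-time coded full-time |

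Examples for the first row: 30 becomes 15, 37.5 becomes 18.75, 59 becomes 29.5; 60 becomes 30 and stays full-time. Examples for the second row: 15 becomes 30, 20 becomes 40, 29 becomes 58; 14 becomes 28 and stays part-time.

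**3. Effect on mean hours.** The documents do not give the share *p* of respondents who answer with a total, so this is an assumption shown over its range, with *p* taken as unrelated to hours worked. For true mean *h*:

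- Treated as weekly: (1 − *p*)*h* + *p*(2*h*) = (1 + *p*)*h*. This runs from *h* at *p* = 0 to 2*h* at *p* = 1; at *p* = 0.5 it is 1.5*h* (+50%).
- Treated as totals: (1 − *p*)(*h*/2) + *p h* = (1 + *p*)*h*/2. This runs from 0.5*h* at *p* = 0 to *h* at *p* = 1; at *p* = 0.5 it is 0.75*h* (−25%).

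If *p* is the same in both arms, both means are multiplied by the same factor. The direction of a difference in mean hours is then kept; its size and the absolute hours are not.

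**4. Repeated job change.** Take a job lost in month 2. Item 17.12 is correctly Yes at 3, 6, 9 and 12 months. Each Yes leads to 17.12.1, which has no no-change option. One event can therefore be entered up to 4 times, of which only the 3-month entry is right for the interval asked about. Elsewhere the same section keeps the periods apart: for GP visits, 17.1 with 17.1.1 covers the time since the event, and 17.2 with 17.2.1 the time since the last assessment.

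**5. Hours lost.** Item 6.1 holds bands, and the Form B copy of 17.13.1 concerns work at the time of the assessment, after the event. A fall from 50 to 32 hours a week stays within the full-time band, and the 18 hours lost (50 − 32) cannot be derived from the coded items.

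**The case against.** Much can be said for the form as it stands.

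- **Reduced hours.** A reader might infer that a drop from 50 to 32 hours a week would appear as no change. The form does not support that: 17.12.1 offers reduced hours as an answer and 17.12.2 asks for an explanation. What is lost is the amount of the reduction.
- **Repeated counting.** A reader might also infer that one job loss will be counted several times in the outcome. Nothing in the protocol says that job changes are summed across visits. Aim 10 is a state at 12 months, and current paid work is asked afresh at 17.13. Read literally, 17.12.1 limits a change to its own interval, and Other with free text is available when nothing new has happened. The form notes at item 9.1 that some options are hidden once ticked, so display rules that the printout does not show may exist.
- **A doubled outcome.** The factor of two applies to one person's numeric hours, not to the productivity outcome as a whole. The outcome also includes status, and its hours are described by way of example as full or part time. People not in paid work have no hours to give.
- **Detection.** Research assistants are trained on the questionnaires and have a Manual of Procedures, which is not shown. An entry of 75, or of 37.5 for someone full-time before the event with no reported change, could be queried.

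These points narrow the concern but do not remove it. Plausible values such as 20 or 40 cannot be assigned to a unit from the number alone, and derivation rules in an analysis plan cannot restore a unit that was never recorded.

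**Conclusion.** The point holds as a minor fault in the wording of the data collection form. Item 17.13.1 lacks a unit, so an individual hours value can differ by a factor of two, with misclassification confined to true weekly hours of 30 to under 60 or of 15 to under 30, depending on how answers are treated. The share of records affected is unknown; the +50% and −25% figures only illustrate an assumed even mix. The mismatch between 17.12 and 17.12.1 matters only if 17.12.1 is used to count or date changes, and the free text may resolve some repeats. Hours lost within a band cannot be computed, although a reduction can be flagged.

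Both arms use the same form, so the main harm is to precision and to absolute productivity costs, with no clear effect on the direction of a between-arm comparison. Current paid-work status and the primary systolic blood pressure endpoint are unaffected.

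**What to change.** - Reword 17.13.1, in both Form B and Form F, to ask for *hours per week usually worked over the past 2 weeks*.
- Give 17.12 and 17.12.1 the same reference period: since the last assessment, and at 3 months since the stroke or TIA. Yes at 17.12 then means that something changed in the interval, and the lack of a no-change option no longer matters.
- Optionally, add a numeric field for pre-stroke hours per week beside Form B item 6.1, so that hours lost can be calculated.

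The cost is the wording of two items and, if wanted, one added field. Answers already collected under the present wording would need a query to the participant or a flag in the data set, since their unit cannot be assumed.

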17.14. Are you currently paying for any private health or support services?

- Yes    No

---

17.14.1. If Yes to 17.14, what services?

---

# S - Recurrent Events and SAE

Participant Registration Number \_\_\_\_\_

### 3. Hospital Admissions

3.1. Was the participant admitted to hospital?

- Yes (completed formal admission procedures)
- No (go to question 4)

3.2. If yes, date admitted to hospital \_\_\_\_\_

3.2.1. Which hospital?

- Auckland
- Middlemore
- North Shore
- Waitakere
- Other

---

3.2.2. If other, please specify.

---

---

3.3. ICD Code for reason for admission

---

---

3.4. Date discharged from hospital (leave blank if still in hospital)

---

#### 4. Stroke / TIA Related Outcomes

---

4.1. Is this a stroke related outcome?

Yes  No

---

4.2. Is this a TIA related outcome?

Yes  No

---

4.3. Recurrent stroke?

Yes  No

---

4.3.1. If Yes, Date

---

---

4.4. Recurrent TIA?

Yes  No

---

4.4.1. If Yes, Date

---

---

4.5. Myocardial Infarction?

Yes  No

---

4.5.1. If Yes, Date

---

---

4.5.2. Could you explain the event?

---

#### 5. Information about death.

---

5.1. Has the participant died?

Yes  No

---

5.2. If yes, date of death

---

---

5.3. If yes, Primary cause of death.

---

---

5.4. ICD Code for Primary cause for death taken from medical record (write all that apply)

---

---

5.5. Secondary contributing factors

---

---

5.6. ICD code for Secondary contributing factors.

---

**6. Sources of Information related to death**

6.1. NZHIS  Yes  
 No

6.2. Medical records  Yes  
 No

6.3. Death certificate  Yes  
 No

6.3.1. If yes, attach a copy of report

6.4. Autopsy performed  Yes  
 No

6.4.1. If yes, attach the copy of report

6.5. Information given by attending doctor  Yes  
 No

6.6. Information given by family/friend  Yes  
 No

6.7. Other  Yes  
 No

6.7.1. If other, please specify

\_\_\_\_\_

**7. SAE due to any aspects of the study protocol intervention**

7.1. Was SAE due to any aspects of the study protocol intervention?  Yes  
 No

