## TRIAL DESIGN

The **Trial of an Individualised Intervention for the Prevention of Stroke (TIIPS)** is a phase III, prospective, open-label, single-blinded end-point randomised controlled trial of 360 participants. The participants will be recruited from Auckland based public hospitals, including outpatient TIA clinics. The recruitment of participants from the existing health system will maximise the uptake of the intervention.

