### Randomisation Procedure

The randomisation form in REDCap will be a hidden form, visible only to the study managers and data manager. The research assistants will not have access to the randomisation form. The randomisation parameters will be predefined, the stratified randomisation module will be selected, and the strata will be selected as: age (<55, ≥55 years), sex (M, F); and four ethnicity categories (1) European, (2) Pacific, (3) Māori, (4) Asian and MELAA (Middle Eastern, Latin American and African). The Dashboard display will show the allocation as HWC or Usual Care.

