### DATA COLLECTION AND FOLLOW-UP

Research assistants (RAs) will be provided training and ongoing supervision to conduct assessments. All assessments will be conducted in a standardised manner in accordance the Protocol. The Project Manager will conduct the randomisation and assign cases to the RAs. RAs will be blinded to the treatment group.

---

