## SERIOUS ADVERSE EVENTS

All hospitalisations (for any reason) are classified as Serious Adverse Events (SAEs), whether or not they are considered related to the health coaching intervention and should be reported to TIIPS study Manager or PI by the Research Assistant as soon as possible by completing a serious adverse event form (Appendix C Form S). If a participant is admitted to hospital, they should notify hospital staff that they are in the TIIPS trial. As this is an open label trial, clinical management should continue as usual.

All serious adverse events will be reported regularly to the Data Safety Monitoring Committee (see below). If at any time the DSMC considers there to be definite evidence of an excess of SAEs they will notify the TIIPS Trial Steering Committee of the findings. The Steering Committee will discuss the issues arising and determine the action to be taken. Copies of the reports issued by the DSMC will be available to Coordinating Centre staff.

An adverse event (AE) is any symptom, sign, illness or experience that develops or worsens in severity during the course of the study. Inter-current illnesses or injuries should be regarded as adverse events. Abnormal results of diagnostic procedures are considered to be adverse events if the abnormality:

- results in study withdrawal
- is associated with a serious adverse event
- is associated with clinical signs or symptoms
- leads to additional treatment or to further diagnostic tests
- is considered by the investigator to be of clinical significance

All adverse events that do not meet any of the criteria for serious should be regarded as non-serious adverse events.

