# APPENDICES

## 38. APPENDIX A: PHYSICAL MEASURES AND EQUIPMENT

### *Requirements for face-to-face visit*

The Participant File with information and consent form.

MoCA hardcopy for cognitive screening.

Tablet or laptop within REDcap database open to 'baseline assessment – physical measurements' (can be used offline if no internet)

Completion of questionnaires in REDCap.

Reminder sheet about blinding of the Research Assistants so that participants do not disclose if they are in the HWC group.

The following will occur at each visit:

Any questions regarding the information sheet or consent form will be addressed, ensuring that the participant received an electronic copy of the consent form to keep and reassured that they can withdraw at any time.

Before the baseline assessment the Research Assistant should review the completed online questionnaires. This will confirm eligibility in terms of medical history before completing further eligibility checks.

The first eligibility check will be the physical measurement of blood pressure (See below under PHYSICAL MEASUREMENTS). If participants have met this criterion, the assessment will continue. The clinical testing will confirm how many biomedical items are in the unhealthy range.

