7.2. If yes, how was the SAE due to the study protocol?

\_\_\_\_\_

8. RA initials  [name]  
 [name]  
 [name]

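### Form S asks the blinded research assistant whether and how an SAE was due to the intervention, which risks unblinding or a poorly informed answer

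*Protocol*

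**What the plan says.** **Blinding.** Trial Design describes a "phase III, prospective, open-label, single-blinded end-point randomised controlled trial of 360 participants". Data Collection and Follow-up states that "RAs will be blinded to the treatment group", and Randomisation Procedure adds that "The research assistants will not have access to the randomisation form"; that form is visible only to the study managers and the data manager. The list of requirements for face-to-face visits in Appendix A includes a "Reminder sheet about blinding of the Research Assistants so that participants do not disclose if they are in the HWC group".

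**SAE reporting.** Under Serious Adverse Events every hospitalisation, related to coaching or not, "should be reported to TIIPS study Manager or PI by the Research Assistant as soon as possible by completing a serious adverse event form". The form is Form S in Appendix C. The Data Safety Management Committee section widens SAEs to new stroke, heart attack, death and serious mood problems.

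**The form.** Section 7 of Form S asks "7.1. Was SAE due to any aspects of the study protocol intervention", with Yes and No as the only answers, and then "7.2. If yes, how was the SAE due to the study protocol". Item 8, directly after, is the RA's initials.

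**The concern.** The intervention under test is coaching, and only the HWC arm receives it. A role that must stay blind is therefore asked to answer, explain and sign a question about a treatment that it must not know the participant received. The protocol assigns this judgement to nobody else, and the form offers no way to leave it open.

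Two things are at stake. The first is the blinded end-point claim. An RA who tries to answer properly has a reason to find out whether the person was coached, and this may happen before the 6-month in-person assessment. Asking could also cut across the Usual Care section, which says that usual-care participants are not told about the HWC intervention. The second is the quality of the relatedness data. An RA who protects the blind will answer some of these items without the fact that matters most.

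**Working it through.** The point rests on no sample size, power or error rate, so there is no stated figure to reproduce. The check sets the instructions side by side.

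1. **Who fills in Form S?** The RA, by the Serious Adverse Events section; the initials field at item 8 agrees.
2. **What may the RA know?** Not the allocation, by Data Collection and Follow-up and by Randomisation Procedure.
3. **What does Section 7 ask?** Whether, and how, the SAE was due to the study intervention. There is no answer for unknown, although Form B offers one at items 1.19, 1.22 and 3.1.1.
4. **Does anyone else make the judgement?** No. The study manager or PI receives the report, but no section asks either of them to assess causality, and the visible part of Form S has no field for a second assessor. I could not see the opening items of the form, before its section 3, and make no claim about them.

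**When does allocation matter for the answer?**

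- An admission with an evident unrelated cause can be answered No in either arm without knowing allocation.
- An event after a procedure done in both arms, such as the capillary blood sample, can also be judged blind.
- For a mood event, or an injury during exercise taken up as a coaching goal, relatedness to coaching depends on whether the person was coached. A Yes with an explanation at 7.2 would usually disclose the arm.

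The conflict is therefore confined to the third group. The documents do not say how large that group is.

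**Can the effect on the primary outcome be sized?** For a shift in mean SBP, the RA must learn the allocation before month 6, the same RA must take the 6-month reading, and that knowledge must move the reading. The protocol gives a rate for none of these steps. Purely as an illustration:

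shift = (share of the HWC arm measured by an unblinded RA) × (bias per reading)

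| Assumed share | Assumed bias per reading | Shift | Relative to the 6 mm Hg target |
|---|---|---|---|
| 0.05 | 1 mm Hg | 0.05 mm Hg | 0.05/6 = 0.8% |
| 0.10 | 2 mm Hg | 0.20 mm Hg | 0.20/6 = 3% |
| 0.25 | 5 mm Hg | 1.25 mm Hg | 1.25/6 = 21% |

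All shares and biases are assumptions. The 25% is borrowed from the Background, where it is an upper figure for adverse outcomes within 90 days of TIA or minor stroke. It does not count SAEs after randomisation, still less unblindings. The last row also needs every such participant to be unblinded and a 5 mm Hg distortion on an automatic monitor. It is an extreme corner, not an estimate.

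**The case against.** The case on the other side has real force, and it rules out several stronger readings that a reader might infer.

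- **Section 7 cannot be answered without knowing the arm.** Too strong. Many hospitalisations can be judged on clinical grounds alone, and the item's wording can be read to cover procedures common to both arms. Nothing tells the RA to ask about coaching. Blind answers are limited, but not worthless.
- **The RA who completes Form S also takes the primary SBP.** Not stated. The recruitment section distinguishes hospital-based from community RAs, and much of Form S consists of facts from records. On the other hand, no rule keeps the two roles apart, and the initials field lists only three options, which hints at a small team without proving overlap.
- **A coaching-related harm would go unnoticed.** Not supported. All hospitalisations are reported regardless of relatedness, and the committee acts on an excess of SAEs. The draft charter in Appendix B gives it unblinded data and adverse-event analyses by coded group (sections on closed sessions and closed reports). No stated analysis or stopping decision uses item 7.1.
- **A known number of participants would be unblinded.** Not supported. Any count needs an assumed SAE rate, and an item appearing on a form is not an unblinding.

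The automatic device, with three readings, also limits what an unblinded RA could do to SBP. It does not protect other outcomes at the same visit that the RA administers or records, such as the MoCA, diet and physical activity.

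What stands is the contradiction in roles. A nearby use of relatedness also remains: the draft charter expects prompt reports of suspected unexpected serious adverse reactions, which need a causality judgement, although it does not say that Form S supplies it.

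**Conclusion.** The point holds in a limited form. The protocol blinds the RA and then has the RA answer and sign a Yes/No causality item on the intervention, with no alternative assessor. For events in which coaching is a plausible cause, this either invites unblinding, possibly before the 6-month assessment, or yields a poorly informed answer.

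The likely bias in the primary comparison is small and cannot be quantified from the documents. Detection of harm by comparing the arms is unaffected. The conclusion rests on the visible text of Form S and on RAs following the SAE section as written. It does not require that the same RA takes the 6-month SBP. It is worth correcting because the contradiction is explicit and cheap to remove, not because it threatens the trial's validity.

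**What to change.** Take Section 7 off the RA's Form S and put it on a separate REDCap form hidden from RAs, as the randomisation form already is. RAs then record event facts only: dates, diagnosis, outcome and sources.

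The study manager completes the hidden form. The manager already sees allocation and is a named recipient of SAE reports. Because those reports now go to the manager or the PI, the SAE section should say that the manager always receives a copy.

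Clinical input should be obtained without releasing allocation to the PI or to anyone who assesses outcomes. One way is for a clinician to judge from the event description whether coaching could have caused the event if the person had been coached; the manager then applies the allocation. Routing allocation to the PI for each SAE would not be a good substitute. The PI would accumulate safety data by arm, which the draft charter reserves to the monitoring committee and the trial statistician.

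The cost is a REDCap permission setting, a short addition to the SAE section, a small added task for the study manager and occasional clinical advice. Visits, sample size and analyses do not change.
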